#### 4.0 Study Endpoints

Outcomes will include vital signs, mood ratings and a cognitive battery assessing neuropsychiatric functioning and symptoms, and will be obtained at baseline, 2, 3, 4, 5, 6, 8 and 12 weeks after treatment. We will also assess feasibility and tolerability.

##### Primary Outcome:

As this is a pilot and exploratory study, the outcomes are largely descriptive. In terms of feasibility we will assess dropout rates and compliance and subjective ratings of the device and the online only study. In terms of safety we will assess changes in blood pressure and any syncope or other adverse events. We will also examine changes in neuropsychiatric symptoms for patients presenting with different NeuroCovid symptoms.

##### Secondary Outcome:

See above.

#### 5.0 Inclusion and Exclusion Criteria/ Study Population

##### Study Population:

Our study population will include adult NeuroCovid patients, who qualify for the study regardless of race or sex. COVID patients will be outpatients. We have the following racial distribution of patients: 66% Black or African American, 30% Caucasian and 2% other; Ethnicity: 2% Hispanic, 98% non-Hispanic. For sex we expect the following: 60% males and 40% females as early data suggest that for some reason males do worse with COVID. We will enroll all patients who qualify regardless of sex, if they or their caregivers consent to the study. We will not include children in this study

##### Inclusion Criteria:

We will enroll subjects who were COVID positive, had some identifiable time of illness, and are home and afebrile. They then must also have some residual new

neuropsychiatric symptom that started after COVID developed. We will also enroll those who were asymptomatic, were tested as COVID positive, and then developed NeuroCovid symptoms. Inclusion symptoms include new onset anxiety, depression, and other CNS symptoms (e.g., vertigo, anosmia, headaches, fatigue, irritability, cognitive processing).

**Exclusion Criteria:**

Damage to left or right ear or anatomy that does not allow tVNS; unstable hemodynamic effects that make a novel clinical intervention unsafe; ischemic or hemorrhagic stroke after developing COVID, patient unable to give consent, or follow instructions, not able to read or write or speak English; no home WiFi.

**6.0 Number of Subjects**

We will recruit 30 COVID positive adults in order to have 24 completers.

**7.0 Setting**

Subjects will be in their home for this trial. MUSC study staff will use an electronic tele-consenting (Doxy.me) and rating platform to communicate with the subjects.

**8.0 Recruitment Methods**

[figure not shown]
We will screen for formerly COVID positive people in our electronic medical record (Epic) who have given permission to be contacted for research. Through our electronic medical record, we will contact MUSC COVID positive patients at least 14 days after their last test, and ask if they have residual symptoms. Subjects will sign consents and complete assessments online. We will then serially administer a broad ranging and comprehensive online battery assessing neuropsychiatric functioning and symptoms. MUSC will ship the device to subjects and they will be educated on the device use. We will provide telemedicine-based device-use support on demand if they have questions.

Please see the attached flyer.

**9.0 Consent Process**

Subjects will sign consents and complete assessments online. Subjects will be consented by Drs. [name] or [name] via a tele-consenting platform.

**10.0 Study Design / Methods**

- Please see the study timeline above. Potential subjects will be phone screened and if appropriate scheduled for a consent meeting and then baseline assessments. They will then be given the video showing how to use the device. MUSC research assistants will then ship a device (and urine pregnancy test) to subjects. They will then have a training session online with MUSC RA's. Then, for each session initially they will do this online with MUSC RA's watching and rating and assisting if needed. They will complete a checklist of how well the subject administers the device. After three sessions if the subject is competent, they will self administer the device after that if they wish. All subjects can ask to have the RA online during any and all treatments if they wish. All sessions are immediately put into the database and the MUSC RA will daily monitor this and make sure the subject has correctly performed the session with no adverse events. If a subject misses a session the RA will call and talk about this. There will be immediate questions before and after each session, as well as the weekly online battery. There are also weekly online assessments and at 4,6,8 and 12 weeks after study start.

*Procedures performed to lessen the probability or magnitude of risks.*

We are excluding subjects with strokes or who are hemodynamically unstable. All sessions will be seated or even reclined if there are problems. Initial sessions are done with the MUSC RA and Soterix staff online. All session data and heart rate are sent immediately to the database and will be checked daily by research staff.

*How all drugs and devices will be used in the research (e.g. dose, dosage form, etc.)*

The device is taVNS applied to the left or right ear at two times the amplitude for perceptual threshold. This intensity of taVNS has been

used in MUSC IRB 1 monitored studies in Parkinson's Disease, Stroke Patients, Newborns and healthy volunteers. The dose for each session is *25Hz, 500us pulse width, 60s ON, 30s OFF, 1 hr. duration.*

Subjects will receive two treatment sessions/day, 6 days per week, for two weeks (randomized), for 24 treatments in the double-blind phase. All subjects will then receive an additional two weeks – 24 more treatments. For those initially randomized to active VNS, they will thus receive up to 48 hours of VNS therapy. For those initially randomized to sham, they will still receive 24 sessions, or 24 hours of treatment. While this may seem like a lot, remember that cervical VNS is implanted and then stimulates on and off for many years. Thus, this dose is minimal compared to the large and safe database of VNS for epilepsy or depression.

*The source records, including medical or educational records that will be used to collect data about subjects.*

We will collect demographic and clinical data from the Epic Database. We will perform phone screens and then online consent and ratings. All ratings will be done online with data going into Redcap with secure access. All data collected from the device will also go to the secure online MUSC Redcap database.

*Describe data collection procedures (e.g. chart review, subject interview, etc.). Provide a description of all assessment instruments to be used. (Upload in eIRB all surveys, scripts, etc.) Include what data will be collected.*

See above. We have uploaded all database questionnaires.

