## **12.0 Data Management**

All data will be stored in the Redcap database. The blind will be kept by the MUSC RA, but they will be blinded as well. Soterix will set the active or sham control from the company after being instructed by the MUSC RA about the randomization code number for that patient, but MUSC will have the unblind in terms of emergency.

Information about the participant (including their identifiable private information and/or any identifiable biospecimens) may have all of their identifiers removed and used for future research studies or distributed to other researchers for future research without additional informed consent from them or their legally authorized representative.

In rare cases, the device manufacturer, Soterix, may need access to minimal PHI (such as name, phone number and address) in the event there is a device malfunction. Well-trained MUSC staff will make every attempt to resolve any issues before putting Soterix in direct contact with the participant.

At a high-level analysis, we will compare the group changes in neuropsychiatric questionnaires in active versus sham taVNS using repeated measures ANOVA from baseline to immediately after last treatment and then as well over the 3-month follow-up.

Power analysis on primary outcome: As there is no real data yet on taVNS effects on NeuroCOVID patients, it is difficult to perform a formal power analysis. The repeated measures design in 15 active and 15 sham patients will allow us to detect differences with a large or moderate effect size to be used for calculating power and sample size for subsequent trials.

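### Baseline is taken before the device is shipped, with no limit on the wait and no full battery scheduled just before the first session, so change from baseline includes time before any stimulation

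*Combined protocol and SAP*

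**What the plan says.** Section 10.0 gives the order of events. After a phone screen, suitable people are "if appropriate scheduled for a consent meeting and then baseline assessments". They then get the instruction video, after which "MUSC research assistants will then ship a device (and urine pregnancy test) to subjects". Next, "They will then have a training session online with MUSC RA's", and the sessions follow. For some women, section 15.0 adds a mailed pregnancy test whose result must be shown to the research assistant.

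The symptom question comes earlier still. Under section 8.0, patients are contacted "at least 14 days after their last test, and ask if they have residual symptoms". The inclusion criteria in 5.0 require a residual new "neuropsychiatric symptom that started after COVID developed", with no severity threshold or minimum duration.

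Aim 1 and section 4.0 each list a single baseline. Section 10.0 also provides that "There will be immediate questions before and after each session, as well as the weekly online battery".

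Section 12.0 compares group changes, active versus sham, "using repeated measures ANOVA from baseline to immediately after last treatment", and then over follow-up. Under the primary outcome, section 4.0 adds: "We will also examine changes in neuropsychiatric symptoms for patients presenting with different NeuroCovid symptoms". Aim 2 asks whether two and four weeks of stimulation differ, without saying how this will be analysed.

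**The concern.** The reference value for every change score is taken before shipping, training and, for some women, a pregnancy test. The wait will differ between patients, and the text neither caps it nor asks for it to be recorded. New symptoms after COVID may still be resolving during that time, so some of the measured change can occur before anyone has received active or sham stimulation.

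Three readings of the data could be affected: the precision of the active-versus-sham contrast, any description of change within an arm, and any within-arm comparison of the first two weeks with the second two. The pilot is meant to supply inputs for later sample-size calculations (12.0), so unnecessary noise or an inflated within-arm change would carry forward.

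**Working it through.** The plan states no figure for the gap or for spontaneous recovery, so there is nothing of its own to reproduce here. The size has to be explored with assumed values.

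**Inputs from the documents.** Controlled period 14 days (Aim 1); 15 patients per arm (12.0); baseline before shipping and training (10.0).

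**Assumed inputs.** A gap of *g* days, taken as 7 to 14 with a wider range of 3 to 21; constant recovery; no treatment effect.

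**Share of the baseline-to-week-2 change that falls in the gap**, *g*/(*g* + 14):
- 3 days: 3/17 = 18%
- 7 days: 7/21 = 33%
- 14 days: 14/28 = 50%
- 21 days: 21/35 = 60%

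If recovery is instead exponential with an assumed half-life of 14 to 56 days, the share is 36% to 45% for a 7-day gap and 54% to 67% for a 14-day gap. A real treatment effect would lower all these shares.

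**Aim 2, if analysed within an arm.** The first interval holds *g* + 14 days of recovery and the second holds 14. The ratio is 21/14 = 1.5 for a 7-day gap and 28/14 = 2 for a 14-day gap, with no treatment effect at all.

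**Simulation with no treatment effect** (20,000 runs, 15 per arm). Assumed: gap uniform on 5 to 14 days; recovery rate with mean 0.2 and SD 0.15 outcome SDs per week; measurement-error SD 0.4 at each rating; analysis of change to week 2.

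| Baseline used | Mean within-arm change | Mean active minus sham | SE of contrast | Type I error |
|---|---|---|---|---|
| Before shipping | 0.67 SD | 0.00 | 0.28 | 5.0% |
| Just before session 1 | 0.40 SD | 0.00 | 0.24 | 5.2% |

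The within-arm figures agree with hand arithmetic. The mean gap is 9.5 days, so 0.2/7 × (9.5 + 14) = 0.67 and 0.2/7 × 14 = 0.40.

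**Source of the lost precision.** The early baseline adds two terms to the variance of a patient's change:
- different recovery rates acting over a longer interval: (0.15/7)² × (23.5² − 14²) = 0.164
- different waiting times: [(0.2/7)² + (0.15/7)²] × 9²/12 = 0.009

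With the later baseline the variance is 2 × 0.4² + (0.15/7)² × 14² = 0.32 + 0.09 = 0.41. The SE is then √(2 × 0.41/15) = 0.23 with the later baseline and √(2 × 0.583/15) = 0.28 with the early one, in line with the simulation. Under these inputs, most of the loss comes from patients recovering at different rates during the wait. The spread of the wait itself contributes little.

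**The case against.** The strongest reply is that the planned comparison is randomised. Both arms share the gap in expectation, so recovery during it cannot favour active over sham. That stands: the simulated difference is zero and type I error about 5% with either baseline. A reader might infer that the early baseline inflates the apparent efficacy of active stimulation against sham. The documents do not support that.

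Second, part of the plan is not visible. Section 10.0 refers to a timeline figure that is not shown and says that the questionnaires were uploaded separately. Section 8.0 speaks of giving the battery serially, in a sentence placed before shipping, which is ambiguous. A reader might infer that the plan rules out a repeat before session 1. It does not say so; one can say only that the available text schedules none. The questions before each session do yield some data before session 1. However, 10.0 lists them separately from the weekly battery, and nothing makes them the reference value.

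Third, the primary-outcome sentence does not say that symptom change will be read within arms, and a later baseline does not make within-arm change interpretable. In the simulation 0.40 SD of null change remains. Both points stand. The later baseline removes only the part that precedes stimulation.

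A reader might also infer that a sizeable share of patients will have lost their qualifying symptom by session 1 and should be excluded. The documents give no resolution rate. The 14 days is a floor on first contact, with screening, consent and baseline still to come, and a patient may have several symptoms. Exclusion at that point would also cost enrolment against the target of 24 completers from 30 recruited.

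**Conclusion.** The point holds in a limited form. The sequence in 10.0 puts baseline before shipping and training, and the available text neither limits the gap nor schedules a full battery just before the first session.

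The consequence for active versus sham is lost precision without bias: an SE of 0.28 against 0.24 under the assumed inputs. Within-arm change, if section 4.0 is read that way, and the first interval of a within-arm analysis for Aim 2, would include recovery before any stimulation. Randomisation does not remove it from those summaries. If Aim 2 is instead analysed by comparing the randomised arms, the gap is balanced in expectation.

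The 33% to 50% is an illustration. It rests on an assumed 7 to 14 day gap, constant recovery and no treatment effect, none of which the documents supply. Section 4.0 calls the study a pilot with largely descriptive outcomes, so the severity is minor.

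**What to change.** - In 10.0, have the patient complete the online battery after training and immediately before the first session, either by moving the existing baseline or by repeating it.
- In 12.0, define that battery as the baseline for the analysis.
- Record the time between any earlier battery and the first session.
- On the same day, record whether the qualifying symptom is still present, as a descriptive variable and not as a new exclusion.

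The ratings are already online, and under section 3.0 the research assistant is already online for at least the first three sessions. Repeating the battery adds at most about 30 completions, one per recruited patient. Moving it adds none, but anyone who leaves before the first session would then have no battery at all. If the unseen timeline already places a battery there, one sentence in 10.0 and 12.0 naming it as the baseline is enough.

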## 1.0 Objectives / Specific Aims

### **Aim 1: Test a home based taVNS protocol for feasibility and efficacy in NeuroCovid patients.**

We will recruit 30 formerly COVID positive adults (ages 18-70) in order to have 24 completers. We will enroll subjects who had a definite case of COVID (were antigen positive) and are at home and are no longer in the hospital. They must also have a residual neuropsychiatric symptom(s) that started anew after COVID developed (NeuroCovid). We will refer to these subjects as 'initially neurocovid and persisting'. We will also enroll those who were asymptomatic, were tested as COVID positive, and then developed NeuroCovid symptoms shortly after their testing. We call these subjects 'initially asymptomatic with later Neurocovid'. (There are several Covid diseases which occur after the acute illness has passed, particular hypercoagulable states and thrombotic strokes and heart attacks.) Symptoms we will target include anxiety, depression, and other CNS symptoms (e.g., vertigo, anosmia, headaches, fatigue, irritability, cognitive processing, etc.). Subjects will be recruited from MUSC electronic records and local testing centers, with online phone screens, consents and ratings. This study is pioneering in being entirely online and home-based. We will provide telemedicine-based device-use support on demand. There will be two experimental groups – initial active taVNS and initial sham stimulation. Subjects will be randomly assigned to each group for a two-week in-home intervention of two hours per day for six days per week of stimulation (active or sham). After the controlled 2-week period, all participants will continue in a 2-week open label arm. Outcomes will include vital signs recorded through the device, mood ratings and a cognitive battery assessing neuropsychiatric functioning and symptoms. These online ratings will be obtained at baseline, taVNS treatment weeks 1-4, and 2-, 4-, 6-, and 8- weeks after treatment. We will also assess feasibility and tolerability. The device will collect daily subjective patient data as well as heart rate, blood pressure and respiration during the treatments.

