## 3.0 Intervention to be studied

We will be using the Soterix Medical Handheld home based taVNS device. Our group has been using taVNS in a variety of clinical laboratory, office or ICU based studies, most of them monitored through this IRB. This is the first MUSC protocol using home based taVNS.

The Soterix device is a research device that is FDA cleared in terms of safety but is not FDA approved for any indication. More information can be found here.

<https://soterixmedical.com/research/tavns>

This IRB and most others have found that taVNS is a minimal risk device and does not require an FDA IDE.

We have attached the device specifications from the manufacturer.

- Cervical VNS is FDA approved for medication resistant epilepsy as well as medication resistant depression (Livanova). FDA pivotal trials are underway for paired cervical VNS with rehab for stroke (microtransponder). Noninvasive

cervical VNS is FDA approved for treating cluster headache (electrocore). To date there are no FDA approved indications for taVNS.

- We will use the device twice daily, six days/week for an initial 2-week double blind phase followed by an additional two weeks active open phase. Thus, subjects will get 24 or 48 actual sessions over 4 weeks. Those randomized to active during the first two weeks will get twice as much overall taVNS as those who get sham during the first two weeks (*25Hz, 500us pulse width, 60s ON, 30s OFF, 1 hr. duration per session*). Subjects will be given a training video to watch and will then have an online training session with the MUSC RA. They will be instructed how to administer the device. For the first 3 sessions at least, the RA will be online watching them do this. They will prepare a checklist of how well the subject is doing the treatment. The patient can then only administer the treatment alone if they are checked off. Treatments will be monitored online for as long as it takes for the participant to be checked off.
- Active stimulation will be in the proper location in the ear. Sham stimulation will be in the same location but there will be a small ramp up of the device, delivering stimulation for 20 seconds, and then it will be programmed to turn off, until the end of the session when it will turn on again for 20 secs.

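### Section 12.0 does not tie the active-versus-sham comparison to the end of week 2, when sham ends; secondarily, the text on company staff at blinded sessions needs reconciling

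*Combined protocol and SAP*

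**What the plan says.** **Design.** Section 1.0 (Aim 1) randomises to active or sham for two weeks, and then: "After the controlled 2-week period, all participants will continue in a 2-week open label arm". Section 3.0 gives the same structure: "initial 2-week double blind phase followed by an additional two weeks active open phase". Section 10.0 counts 24 treatments in the blinded phase and a further 24 for everyone, so up to 48 hours of active treatment for those who start on active and 24 for those who start on sham. Aim 2 uses weeks 3-4 to compare two with four weeks of stimulation. It also says that the blind is kept while everyone receives active treatment.

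**Analysis.** Section 12.0 compares group changes in the neuropsychiatric questionnaires, active against sham, by "repeated measures ANOVA from baseline to immediately after last treatment and then as well over the 3-month follow-up". It adds that the effect size from 15 patients per arm will feed power and sample-size calculations for later trials. No section names a week-2 comparison.

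**Ratings.** Aim 1 lists baseline, treatment weeks 1 to 4, and 2, 4, 6 and 8 weeks after treatment. Section 10.0 has weekly ratings and then 4, 6, 8 and 12 weeks from study start. Section 4.0 lists baseline and 2, 3, 4, 5, 6, 8 and 12 weeks, all described as after treatment.

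**Company staff.** Section 12.0: "Soterix will set the active or sham control from the company after being instructed by the MUSC RA about the randomization code number". The risk-reduction paragraph of section 10.0: "Initial sessions are done with the MUSC RA and Soterix staff online". Section 3.0 mentions only the research assistant (RA): "For the first 3 sessions at least, the RA will be online watching them do this". So does the procedure paragraph of section 10.0: "for each session initially they will do this online with MUSC RA's watching and rating and assisting if needed". Section 12.0 treats company contact as a fallback: "Well-trained MUSC staff will make every attempt to resolve any issues before putting Soterix in direct contact with the participant".

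**The concern.** Sham exists only in weeks 1-2, so only ratings up to the end of week 2 compare active with sham. Neither analysis window in section 12.0 stops there. If the text is followed as written, the result labelled active versus sham is the difference between an arm with four weeks of active stimulation and an arm with two. That is the Aim 2 question.

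The outcomes are largely descriptive, but this effect size has a stated use: planning the next trial. A sham-controlled follow-on trial needs the sham-controlled effect, and section 12.0 does not say that this is the one to be carried forward.

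The secondary matter concerns the same two weeks. The company sets the arm, and one sentence puts company staff online at initial sessions. The blinding statement in section 12.0 covers the RA and does not mention company staff. The questionnaires are completed online by the participants, so the plan should be clear about who is present and what they know.

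**Working it through.** **1. Session counts (sections 3.0 and 10.0).** Two sessions a day × 6 days × 2 weeks = 24 per phase, which reproduces the plan's figure.

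| Time | Initial active | Initial sham | Difference in active sessions |
|---|---|---|---|
| End of week 2 | 24 | 0 | 24 |
| End of week 4 | 24 + 24 = 48 | 0 + 24 = 24 | 24 |

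The arms differ by 24 active sessions at both times, but only the first row has a comparator without active treatment.

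**2. Which treatment is last.** Section 10.0 counts the weeks 3-4 sessions as treatments, and section 18.0 has the device returned after four weeks. The literal last treatment is therefore at the end of week 4.

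**3. Which ratings enter.** On the Aim 1 schedule there are 4 + 4 = 8 post-baseline ratings. Those at weeks 1 and 2 are sham-controlled; the other 8 − 2 = 6 come after both arms have started active stimulation. In the first window (baseline to week 4), 2 of 4 post-baseline ratings are sham-controlled; over the whole follow-up, 2 of 8. A repeated measures model on the weekly ratings would thus include the sham-controlled data, but pooled with both-active data and with no week-2 contrast named.

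The schedules also conflict. Aim 1's last rating is at 4 + 8 = 12 weeks from the start, which agrees with section 10.0. Section 4.0, read literally, has no rating during treatment.

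**4. Consequence for a follow-on trial.** The statement in section 12.0 about detectable effects cannot be reproduced, because no alpha, power, SD or correlation is given. None is needed for a ratio. For a two-arm comparison of means, n per arm = 2(z₁₋α/₂ + z₁₋β)²/d². If the standardised week-4 effect is r times the week-2 effect, alpha and power cancel:

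n(week 4) / n(week 2) = 1/r²

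| r (assumed) | Ratio |
|---|---|
| 1.25 | 1/1.5625 = 0.64 |
| 1.0 | 1.0 |
| 0.75 | 1/0.5625 = 1.8 |
| 0.5 | 1/0.25 = 4.0 |

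r = 1 if benefit rises equally with every active session. r < 1 if benefit levels off and the initial-sham arm catches up. r > 1 if benefit is delayed or accelerates. As one example, suppose benefit approaches a plateau as 1 − exp(−ks), with 25% of the plateau reached at 24 sessions. At 48 sessions it is 1 − 0.75² = 0.4375, so r = (0.4375 − 0.25)/0.25 = 0.75. With 50% reached at 24 sessions, r = (0.75 − 0.50)/0.50 = 0.5.

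**5. Company staff.** Set side by side, one sentence in section 10.0 has them at initial sessions, section 3.0 and another paragraph of section 10.0 name only the RA, and section 12.0 makes contact a fallback. The initial sessions fall in the blinded phase. No text says whether attending staff have the allocation or differ from those who set it. No size can be computed.

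**The case against.** The best defence is context. Section 12.0 describes a high-level analysis of active against sham, which can exist only in the controlled two weeks, and Aim 2 states the two-versus-four-week question separately. The last treatment may therefore mean the last blinded one. That is possible, but section 12.0 does not say so and section 10.0 counts the later sessions as treatments. The timeline figure was not readable in the text available here and may settle the rating times.

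A reader might infer that the analysis stops at week 4 or that the sham-controlled data are lost. Neither is supported. The same sentence continues to the 3-month follow-up, and weekly ratings from weeks 1-2 would be available to the model. The gap is the missing contrast.

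A reader might also infer that week 4 must understate the effect. The documents give no dose-response information; r = 1 is a live case and r > 1 cannot be excluded.

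On company staff, the tempting reading is that people who know the arm sit in on blinded sessions. The documents do not show this. Attendance is itself in doubt, and nothing says that attendees know the arm. Their presence is listed among measures that reduce risk, which is a reason to clarify the role and not to assume that it does harm.

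**Conclusion.** The main point holds. Followed literally, section 12.0 estimates 48 against 24 active sessions and calls it active versus sham, and no section names the week-2 comparison. The direction and size of the discrepancy are unknown. The 1/r² range of 0.64 to 4.0 rests on assumed values of r from 1.25 to 0.5 and on sizing the next trial with a simple comparison of two means. It illustrates what is at stake and is not an estimate of bias. The pilot's descriptive purpose limits the weight of this, but the declared use of the effect size makes the definition worth settling.

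The secondary point supports only a request to reconcile the text on company attendance and to state the blinding of anyone who attends. It is not evidence that the blind is broken.

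**What to change.** - In section 12.0, name baseline to the end-of-week-2 rating as the active-versus-sham comparison and as the source of the effect size for later trials. Report week-4 and follow-up results separately, as comparisons by initial allocation after both arms have had active stimulation (Aim 2).
- Reconcile the rating schedule in section 4.0 with Aim 1 and section 10.0, so that the on-treatment week-2 rating is unambiguous.
- Reconcile the description of weeks 3-4 as open (Aim 1, section 3.0) with the statement in Aim 2 that the blind is kept, and say what participants and raters know in that period.
- Reconcile sections 3.0, 10.0 and 12.0 on whether company staff attend initial sessions. If they attend before the week-2 rating, state that those attending do not have the allocation.

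**Cost.** The first three changes are wording only, since Aim 1 and section 10.0 already plan weekly ratings. The downside is that the sham-controlled estimate covers two weeks, and durability is reported without a sham comparison, as the design already implies. The fourth may require the company to separate the people who set the arm from those who attend. Attendees could then not open the arm setting to troubleshoot during that period. The documents do not say whether the company can arrange this.
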